5.5 RANDOMISATION

5.5.1 Randomisation Procedures

The electronic randomisation system and trial database are hosted by the University of Nottingham. Randomisation involves minimisation on key prognostic factors including: age, sex, stroke severity (NIHSS), dependency resulting from the stroke, systolic blood pressure $\leq/ > 140$, smoker status, time after stroke, years of education. Years of education give an estimate of pre-morbid cognitive ability and predicts post-stroke cognitive impairment; BP and smoking predict recurrent stroke; delay since stroke reflects disease activity; age, sex and stroke severity are standard minimisation variables. This approach ensures concealment of allocation (note allocation concealment means that it is not possible to guess which treatment the next patient will be randomised to), minimises differences in key baseline prognostic variables, and improves statistical power. Randomisation will not be minimised by Centre because this may result in high rates of allocation prediction, but a pre-specified post-hoc analysis by centre will be performed to investigate and adjust for heterogeneity of treatment effect by centre.

Randomisation will allocate a trial treatment, which will be prepared by the local participating Pharmacy.

Note that randomisation will be performed during normal office hours (09.00 – 17.00) and the trial allows for randomisation to occur months or years after the stroke. Therefore, in the event of computer failure (for example: server failure), the investigator will wait until the computer system is re-established to perform the randomisation. Normally, this would only be a few minutes to two hours. However, if this delay requires the patient to return on a separate occasion to collect the drugs, then a separate appointment will be made and the patient's travel expenses covered as per other trial visits.

Patients will be randomised to one of the following at a 1:1 ratio as per Section 6.2:

- cilostazol versus no cilostazol
- isosorbide mononitrate versus no isosorbide mononitrate

resulting in a partial factorial comparison of cilostazol versus isosorbide mononitrate versus both drugs versus neither drug.

The randomisation algorithm will allocate a unique identifier which will be used to label the treatment pack containing the appropriate drug made up for the patient and dispensed by the local Pharmacy.

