- or, if no visible acute lacunar infarct, there is no competing pathology as a cause for stroke (e.g. no acute cortical infarct, no acute lacunar or cortical intra-cerebral haemorrhage, no stroke mimic such as tumour, subdural haematoma). Scans will be sent for central reading.

Cognitive baseline testing: Patients will be assessed at baseline using the Montreal Cognitive Assessment (MoCA), the timed Trail Making Test B for processing speed/executive function, and ZUNG for mood. Their years in full time education will be recorded.

Symptoms and adverse effects: Will be assessed using a structured validated questionnaire to assess for recurrent neurological symptoms and whether these meet clinical criteria for TIA or stroke, angina or MI, peripheral vascular disease (and details thereof), headache, dizziness,

palpitations, altered bowel habit, and adherence to medication, and if any other symptoms have occurred. The patient will be asked whether were severe enough to interfere with normal daily activities. Patients will also be able to report any other symptoms and describe them in detail. Depending on the time point in the study this will either be completed face to face at a study visit or by telephone.

Tablet adherence: Will be assessed by asking the patient about their medication usage and recording the details in the eCRF. In addition, patients will be asked to return any packs of unused tablets to the hospital pharmacy at the end of the trial. All returned tablets will be counted at Pharmacy and then be destroyed.

Blood pressure: Will be assessed using a validated clinical instrument that meets British Hypertension Society standards.

Haematology and biochemistry: Full blood count, urea and electrolytes and renal function will be obtained from the most recent sample obtained since the time of the index stroke. If there is a clinical reason to expect change in which case the full blood count and biochemistry should be repeated prior to randomisation. These samples will be analysed in the hospital haematology or biochemistry labs in the centre in which the patient has been recruited.

Neurological outcomes: Information on recurrent stroke, TIA, angina, MI, PVD will be assessed by postal or phone questionnaire at 6 and 12 months. Patients will be encouraged to seek medical advice if they develop new neurological events during the trial.

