Functional outcome: modified Rankin Scale to assess dependency at 6 and 12 months. If participants are unable to be contacted, the central assessor will obtain the most recent modified Rankin Score from the local staff (if available).

Cognitive outcomes: Telephone MOCA, Telephone Interview for Cognitive Status (TICS), mobility and physical functioning sections of the Stroke Impact Scale and the ZUNG will be collected remotely at six and 12 months by the central trial team. TRAILS B will be repeated when attending for 1 year MR in Centres that are able to do this. TICS will be collected for consistency with prior and ongoing trials (ENOS, TARDIS, RIGHT 2, TICH) and good comparability.⁶² TMOCA will be collected for comparison with TICS for potential use in future trials as it purports to assess executive function more than TICS. IQCODE will be collected from the relative/partner/carer by post or phone.

Health economics: EQ-5D-5L, EQ-VAS, return to work, hospitalisation, need for long term supportive care will be collected at 12 months.

Follow-up Brain MRI: all patients will have repeat brain MRI at 12 months to assess burden of WMH, microbleeds, lacunes, new infarcts or haemorrhage and atrophy and where feasible to assess diffusion tensor tissue parameters. These scans will be sent to Edinburgh for central blinded adjudication.

Follow-up at 6 and 12 months will be by post and telephone, blinded to allocated treatment. A trained assessor who is part of the central trial team and based either at the University of Edinburgh or University of Nottingham and who is blinded to treatment and baseline clinical information, will first confirm with the GP that the participant is contactable. They will then contact the patient or carer by post and phone to administer the questionnaires following a standardised script.

In addition to the assessments detailed above, participants will receive one to five informal contacts over the duration of their trial participation. One will consist of a participant newsletter and any other informal contacts will be a brief phone call or additional participant newsletter. During those contacts, a member of the central or site teams will update participants on the trial status, thank them for their continued help with the study, and give them an opportunity to ask questions.

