9.2 PROPOSED ANALYSES

We will compare cilostazol v no cilostazol, ISMN v no ISMN, cilostazol and ISMN v neither. The proportion completing to target dose and any adverse events will be assessed using odds ratios. The LACI-2 will focus on numbers recruited, retained, tolerance and safety outcomes, blinded for TSC and unblinded intention to treat (ITT) for DMC. Safety analysis will use: Kaplan-Meier and Cox proportional regression for analysis of time-to-event outcomes of death; binary logistic regression for SAEs, recurrent stroke, MI, and in those completing 12 month MRI, the amount of microbleeds, siderosis, new infarcts, WMH burden; all adjusted for minimisation variables to maximise power.⁶⁷ We will collect data for future health economics analysis (EQ-5D-5L, EQ-VAS).

A secondary ITT analysis will be performed using logistic regression adjusted for minimisation variables of cilostazol+/-ISMN versus control on efficacy and safety outcomes, with secondary tests of subgroup interactions. Ordinal logistic regression will be used for ordinal categorical outcomes (e.g. mRS) to increase power.⁶⁸

A Statistical Analysis Plan (SAP) will be published prior to database lock and will describe analysis procedures and procedures for missing, unused or spurious data, and definitions of populations analysed.

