Haematology (full blood count) and Biochemistry (urea, electrolytes, creatinine) – most recent value obtained since time of index stroke is acceptable unless clinical reason to expect change		X ^s				
Blood pressure		X ^s				X ^s [‡]
Cognitive test: document years of education; Montreal Cognitive Assessment (MOCA)		X ^s				
Timed Trail Making Test B		X ^s				X ^s [‡]
Dispense trial medication ²		X ^s			X ^s	
Structured questionnaire: symptoms; medication history and IMP tablet adherence			X ^s	X ^s	X ^c	X ^c
Structured questionnaire: recurrent vascular events, mRS, TICS, t-MOCA, SIS, ZUNG					X ^c	X ^c
Obtain IQCODE (post/phone) from relative						X ^c
Follow-up brain MRI						X ^s
Health Economics data: EQ-5D-5L, EQ-VAS						X ^c
Adverse event / con meds reporting as necessary			X ^s	X ^s	X ^{s,c}	X ^{s,c}

[†] Consent will be obtained before the data collection procedures commence or randomisation is performed. Randomisation occurs at the end of the baseline visit.

[‡] at 12 months in some centres only.

² Dispensing in 3-monthly intervals is allowed.

^s Assessment performed by local site team.

^c Assessment performed by blinded assessor who is part of the central trial team.

SIS: Stroke Impact Scale; TICS: telephone interview for cognitive status; t-MOCA: telephone MOCA.

SECTION 4. STATISTICAL PRINCIPLES

Confidence and p values**16 Level of statistical significance**

The results of analyses and comparisons will be shown with $p < 0.05$.

17 Multiplicity

No adjustment will be made for multiplicity.

18 Levels of confidence intervals

The results of analyses and comparisons will be shown with 95% confidence intervals.

19 Adherence

19a Definition: 75% of patients will be able to tolerate trial medication, in at least half dose, up to one year after randomisation (i.e. less than 25% will stop trial medication completely through inability to tolerate the drugs).

19b Adherence presentation: See Table 4.

19c Protocol deviations: Protocol violations will be reported to the sponsor within 24 hours of becoming aware of the violation. Protocol deviations will be recorded in a protocol deviation log with these submitted to the sponsors every 3 months.

19d Protocol deviation presentation: Listing of violations and deviations and their frequency.

20 Analysis populations

Three populations are defined:

1. Intention-to-treat: All consented participants with a primary outcome measure.

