- Death, including fatal haemorrhage, aiming for less than outside the upper 95% CI of 2% per year.
- The *combined rate* of recurrent stroke, MI, death, cognitive impairment and dependency, aiming for 40-50% at one year after enrolment.

Comparison of rates of events between the treatment groups: cilostazol vs no cilostazol, ISMN vs no ISMN, and cilostazol and ISMN vs neither, for:

- Systemic or intracranial bleeding, recurrent cerebral and systemic vascular events, and vascular and non-vascular causes of death.
- Death, all cause.
- New ischaemic or haemorrhagic stroke lesion or increase in SVD lesions on MRI.
- Composite of: recurrent clinically-evident stroke, MI, death, cognitive impairment (including dementia) and dependency.
- Individual event: stroke (clinically-evident or imaging-detected ischaemic or haemorrhagic stroke to be reported separately), TIA, myocardial ischaemia, cognitive impairment and dementia.
- New infarcts and haemorrhages, absolute and change in WMH, microhaemorrhages, lacunes, atrophy imaging variables from central read of baseline imaging and one year MRI
- The comparisons of combined cilostazol and ISMN versus neither, whilst being very underpowered statistically, are presented since these may be the two groups studied in the planned follow-on trial.

Central tendency, comparisons and regressions will be analysed as follows (**Table D**).

Table D. Descriptive and analytical statistics

	Binary	Nominal	Ordinal	Continuous
Central tendency and distribution	N (%)	N (%)	Median [interquartile range]	Mean (standard deviation)
Comparisons	Chi-square (2x2)	Chi-square (2x2, or rxc)	Mann-Whitney U or Kruskal-Wallis	t-test (pooled) or 1-way ANOVA
Regression	Binary logistic regression (BLR)	-	Ordinal logistic regression (OLR)	Multiple linear regression (MLR)

27b Covariate adjustment: Analyses will be adjusted for minimisation covariates:

- Age, sex, stroke severity (NIHSS), dependency resulting from the stroke, systolic blood pressure, smoking status, time after stroke, years of education.

Covariate adjustment with continuous variables (age, NIHSS, SBP, time after stroke, years of education) will use original, not dichotomised, data.

27c Assumption checking: The assumption of proportionality will be tested using the likelihood test.

27d Alternative methods: If the data fail the assumption of proportionality (tested using the likelihood test), we will use alternative methods such as multiple logistic regression.

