Myocardial infarction		XX (X)
Cognitive impairment		XX (X)
Dependency, mRS>2		XX (X)
Any of these	40-50%	XX (X)

Table 3. Clinical Outcomes at 12 months.

Data are number (%), median [interquartile range] or mean (standard deviation). Analyses performed using binary logistic regression (BLR), ordinal logistic regression (OLR) or multiple linear regression (MLR) with adjustment for age, sex, time from stroke onset to randomisation, years of education, smoking status, and baseline mRS (dependency), stroke severity (NIHSS) and systolic blood pressure. Mean (SD) and MLR will be used instead of median [IQR] and OLR for ordinal scales with more than 7 levels (central limit theorem/large sample). The Wei-Lachin test is used to analyse multiple outcomes in parallel.

Number	ISMN	No ISMN	Difference (p)	Cilostazol	No cilostazol	Difference (p)	ISMN + Cil	Neither	Difference (p)
Composite									
Stroke	XX (X)	XX (X)	CPHR BLR	XX (X)	XX (X)	CPHR BLR	XX (X)	XX (X)	CPHR BLR
TIA	XX (X)	XX (X)	BLR	XX (X)	XX (X)	BLR	XX (X)	XX (X)	BLR
MI	XX (X)	XX (X)	BLR	XX (X)	XX (X)	BLR	XX (X)	XX (X)	BLR
Cognitive impairment	XX (X)	XX (X)	BLR	XX (X)	XX (X)	BLR	XX (X)	XX (X)	BLR
Dependency, mRS>2	XX (X)	XX (X)	BLR	XX (X)	XX (X)	BLR	XX (X)	XX (X)	BLR
Death	XX (X)	XX (X)	BLR	XX (X)	XX (X)	BLR	XX (X)	XX (X)	BLR
Cognition									
Cognition, 7 level Normal	XX (X)	XX (X)	OLR	XX (X)	XX (X)	OLR	XX (X)	XX (X)	OLR
Minor, single domain	XX (X)	XX (X)		XX (X)	XX (X)		XX (X)	XX (X)	
Minor, multi-domain	XX (X)	XX (X)		XX (X)	XX (X)		XX (X)	XX (X)	
Major, mild	XX (X)	XX (X)		XX (X)	XX (X)		XX (X)	XX (X)	

LACI-2 SAP V1.5

06/06/2022

Major, moderate	XX (X)	XX (X)					
Major, severe	XX (X)	XX (X)					
Death	XX (X)	XX (X)					
Cognition, 4 level							
Normal	XX (X)	XX (X)					
Minor	XX (X)	XX (X)					
Dementia	XX (X)	XX (X)					
Death	XX (X)	XX (X)					
Memory/thinking problem	XX (X)	XX (X)	BLR	XX (X)	XX (X)	BLR	XX (X)
MoCA	XX (X)	XX (X)	MLR	XX (X)	XX (X)	MLR	XX (X)
TICS-m	XX (X)	XX (X)	MLR	XX (X)	XX (X)	MLR	XX (X)
Verbal fluency, animal naming	XX (X)	XX (X)	MLR	XX (X)	XX (X)	MLR	XX (X)
Trails B, time	XX (X)	XX (X)	MLR	XX (X)	XX (X)	MLR	XX (X)
Trails B, points	XX (X)	XX (X)	MLR	XX (X)	XX (X)	MLR	XX (X)
Dementia, clinical diagnosis	XX (X)	XX (X)	BLR	XX (X)	XX (X)	BLR	XX (X)
Clinical							
Systolic BP (mmHg)	XX (X)	XX (X)	MLR	XX (X)	XX (X)	MLR	XX (X)
Diastolic BP (mmHg)	XX (X)	XX (X)	MLR	XX (X)	XX (X)	MLR	XX (X)

LACI-2 SAP V1.5

06/06/2022

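### The 12-month cognitive outcomes are adjusted only for the eight minimisation variables; adding baseline MoCA and Trails B, already collected, would recover some efficiency on secondary outcomes

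*SAP*

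**What the plan says.** SAP 27b adjusts for the minimisation covariates, listed as "Age, sex, stroke severity (NIHSS), dependency resulting from the stroke, systolic blood pressure, smoking status, time after stroke, years of education". The legend of SAP Table 3, which holds the 12-month cognitive outcomes, names the same eight. Protocol 9.2 uses the same set and, for the safety models, gives the reason: "all adjusted for minimisation variables to maximise power". The only cognition-related member is education, of which Protocol 5.5.1 says "Years of education give an estimate of pre-morbid cognitive ability and predicts post-stroke cognitive impairment".

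Baseline cognition is measured. Protocol 7.2 and SAP Table C schedule MoCA at the baseline visit together with "the timed Trail Making Test B for processing speed/executive function", and SAP Table 1 tabulates both by arm. At 12 months the central team collects "Telephone MOCA, Telephone Interview for Cognitive Status (TICS), mobility and physical functioning sections of the Stroke Impact Scale", and "TRAILS B will be repeated when attending for 1 year MR in Centres that are able to do this".

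No other section puts a baseline cognitive score into a model. SAP 27e confines its sensitivity analyses to the primary outcome, and 27f concerns subgroups of the composite. SAP Section 7 lists cognitive ability at randomisation among the measured variables relevant to the composite, but makes it no model term.

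**The concern.** A baseline measurement of the outcome is often its best single predictor. The plan has this for some outcomes: 12-month mRS is adjusted for baseline mRS, and 12-month systolic pressure for baseline systolic pressure, because both happen to be minimisation variables. Cognition gets only years of education. Baseline MoCA should be prognostic here. Protocol section 3 sets no minimum cognitive score for entry, and SAP Table E classifies 12-month cognition largely by absolute thresholds, so a patient who enters with a low score can be classed as impaired at 12 months without having declined.

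At stake is efficiency on secondary outcomes. The feasibility endpoint and the event rates tabulated for phase III do not depend on this choice.

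**Working it through.** **The plan's own figures.** The documents state no power or precision for cognition. The related stated calculation is phase III model D (45% v 36%, 80% power, two-sided 5%). It gives n′ = [1.960√(2×0.405×0.595) + 0.842√(0.2475+0.2304)]²/0.09² ≈ 466 per arm. With the Fleiss correction this is 488 per arm, total 976 as stated. Nothing below disputes it.

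**Inputs.** N = 363 recruited (SAP Table 2), taken as split 1:1 with everyone analysed, which is optimistic. Cognitive impairment 30% (SAP Table A). Relative reduction 20%, borrowed from the phase III assumption, so 0.30 × 0.8 = 24%. The partial correlation r between baseline and 12-month score, given the eight covariates, is not in the documents; 0.2 to 0.7 is assumed.

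**Linear outcomes** (telephone MoCA, TICS-m, Trails B). The variance of the treatment effect is multiplied by 1 − r². In units of the residual SD after the eight covariates, the 95% half-width is 1.96 × √(2/181.5) × √(1 − r²), and the difference detectable with 80% power is 2.802 × √(2/181.5) × √(1 − r²).

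| r | 1 − r² | Equivalent N, 363/(1 − r²) | Half-width | Detectable |
|---|---|---|---|---|
| 0 | 1.00 | 363 | 0.206 | 0.294 |
| 0.2 | 0.96 | 378 | 0.202 | 0.288 |
| 0.3 | 0.91 | 399 | 0.196 | 0.281 |
| 0.5 | 0.75 | 484 | 0.178 | 0.255 |
| 0.7 | 0.51 | 712 | 0.147 | 0.210 |

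The change from in-person to telephone testing lowers r for MoCA. If r would be 0.5 on the same test and the switch scales it by an assumed 0.7 to 0.9, r is 0.35 to 0.45 and the cut is 12% to 20%.

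**Binary and ordinal outcomes.** Simulation, 4,000 trials per r, N = 363, Monte Carlo error about 0.8 points per power. The 7-level case assumes levels of 55/12/10/12/6/3/2% and a true effect of 0.22 latent SD.

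| r | Binary power, without → with | SE of log OR, without → with | 7-level power, without → with |
|---|---|---|---|
| 0.2 | 29.1 → 29.9% | 0.266 → 0.271 | 53.5 → 54.8% |
| 0.3 | 29.6 → 30.8% | 0.266 → 0.275 | 53.8 → 56.6% |
| 0.5 | 29.3 → 33.3% | 0.266 → 0.291 | 53.1 → 63.5% |
| 0.7 | 28.4 → 39.0% | 0.266 → 0.328 | 52.5 → 76.1% |

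The standard error rises, but the conditional log odds ratio moves away from zero by more, so power rises while the interval widens. In the 7-level case the odds ratio moves from 0.64 to 0.63/0.62/0.59/0.52. A second binary simulation with a larger assumed effect (0.3 latent SD, 1,500 trials) shows the same pattern: power 55.8 → 57.4%, 55.5 → 61.3% and 54.1 → 70.3% at r = 0.3, 0.5 and 0.7, with SE 0.247 → 0.254/0.269/0.301.

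**Dual versus neither.** About half of 363. For the binary case at r = 0.5, the non-centrality without MoCA is 1.960 − 0.545 = 1.415; divided by √2 it is 1.001, and power is Φ(1.001 − 1.960) ≈ 17%. With MoCA it is 1.528/√2 = 1.081, and power is Φ(−0.879) ≈ 19%.

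**Missing baseline scores**, assumed share m = 10%. An allocation-blind fill-in gives a variance ratio of 1 − r²(1 − m); the complete-case rule of SAP 20 gives (1 − r²)/(1 − m).

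| r | Fill-in | Complete case |
|---|---|---|
| 0.2 | 0.964 | 1.067 |
| 0.3 | 0.919 | 1.011 |
| 0.5 | 0.775 | 0.833 |
| 0.7 | 0.559 | 0.567 |

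Under complete cases, adjustment does harm at r = 0.2 and gains nothing at 0.3.

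**The case against.** The adjustment set was pre-specified in the protocol and the SAP follows it. Protocol 9.1 puts tolerability and safety first and derives the 400 from the death rate, so no precision target for cognition is missed. The gain rests on a correlation nobody has stated. The efficacy endpoints named in SAP 26a are cognitive impairment and dementia; Table 3 analyses impairment and clinically diagnosed dementia by logistic regression, where the benefit is smallest. The 7-level scale is partly defined by mRS, care-home status and death, and baseline mRS and NIHSS are already covariates, so r may be low there. The change also needs an exception to the SAP's missing-data rule.

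All of this stands. It makes the point an optional improvement with a range for its size; it does not remove the improvement.

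Four stronger readings are tempting, and the documents support none of them:
- **That the planned estimates are biased.** Randomisation protects them; a prognostic covariate left out costs efficiency only.
- **That every cognitive estimate would become more precise.** That holds literally for the linear models only; on the log-odds scale the interval widens.
- **That adjustment would rescue the dual-versus-neither comparison**, which SAP 27a concedes is badly underpowered. The 17% to 19% above shows otherwise.
- **That SAP Section 7 contradicts 27b.** Section 7 lists example variables and commits no model to them. It shows that the authors regard baseline cognition as relevant.

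**Conclusion.** The point holds as a low-cost improvement, not as the correction of an error. For the linear cognitive outcomes the variance of the treatment effect would fall by r²: 4% to 49% over an assumed r of 0.2 to 0.7, and not at all if the baseline score adds nothing to the eight covariates. The lower values are likelier for MoCA because the instrument changes; Trails B is the same test both times, but only some centres repeat it. For binary cognitive impairment the gain is about 1 to 4 points of power at r up to 0.5 in the 30% v 24% case, and the smallest of these gains are close to simulation error. The 7-level scale gains about 1, 3 and 10 points at r = 0.2, 0.3 and 0.5 under an assumed level distribution. The comparison-level figures assume all 363 patients contribute. The proportional variance cut does not depend on N; the power figures do, and would be lower after losses and single-drug randomisation.

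**What to change.** Amend SAP 27b and the Table 3 legend before unblinding:

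1. Add continuous baseline MoCA to the models for 12-month telephone MoCA, TICS-m, the 7- and 4-level cognition scales and cognitive impairment.
2. Add baseline Trails B to the model for 12-month Trails B, in the centres that repeat it.
3. As a stated exception to SAP 20, fill in missing baseline scores by a rule that ignores allocation, for example the overall mean plus a missing indicator, so that no patient is dropped. This matters because SAP 26c derives the MoCA trail item from Trails B, so a missing Trails B also leaves MoCA incomplete.
4. Keep the minimisation-only model as a sensitivity analysis, and say that odds ratios from the two models are not directly comparable, because conditional odds ratios change when a covariate is added.

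The cost is a few lines of SAP text, one extra model per outcome and a small departure from the no-imputation rule. No new data are needed.

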8b Secondary Objectives: To assess drug tolerability, safety, recruitment rates and accuracy, outcome event rates and retention in preparation to a large phase III randomised controlled trial to prevent recurrent lacunar stroke and physical and cognitive impairment.

This SAP focuses on these primary and secondary objectives. Planned follow-on publications will address tertiary questions.

SECTION 3. STUDY METHODS

9 Trial design

Prospective randomised open-label blinded end-point (PROBE) partial-factorial phase IIb/c trial aiming to recruit 400 patients recruited in UK Stroke Network Centres, with follow-up to one year.

10 Randomisation: By central computer-generated allocation at the University of Nottingham with minimisation on key prognostic factors: age, sex, stroke severity (NIHSS), dependency resulting from the stroke, systolic blood pressure $\leq/ > 140$ mmHg, smoking status, time after stroke, and years of education.

11 Sample size/power considerations

Conservatively, we have used sample size calculations based on binary measures. Use of ordinal measures at the time of analysis will increase statistical power.

11a Event rates: Annual event rates (Table A) were assessed from trials (SPS3,⁵ lacunar patients in ENOS,^{6 7} IST-3^{8 9}) and observational data (LADIS;¹⁰ our¹¹⁻¹³ and other¹⁴ studies). All-cause death rates were assumed to be 2.0% with upper 95% CI of 4% in 400 patients.⁵ Hence, the sample size was set at 400 participants.

Table A Annual absolute risks (%) of outcome events after lacunar stroke

Vascular death	Non-vascular death	Non-fatal IS or TIA	Non-fatal ICH	MI	MACE	Dependent (mRS 3-5)	Cognitive impairment	Dementia
1.8	0.5	2.5	0.5	0.6	3	15	30	15

ICH: intracerebral haemorrhage; IS: ischaemic stroke; MACE: major adverse cardiac events; MI: myocardial infarction; mRS: modified Rankin scale; TIA: transient ischaemic stroke

11b Comparison of two groups in a future phase III trial: Assuming power 0.80, alpha=0.05, 1:1 randomisation, composite event rate (MACE, dementia, non-vascular death, new MRI signs) 45% and absolute reduction 9% (relative risk reduction 20%), and loss to follow-up 10%, a sample size of 1100 will be needed. A

number of outcomes are relevant to patients with SVD and using these has implications for the sample size (Table B).

Table B. Sample size for composite outcome in main trial using estimated event rates.¹

Composite model	A	B	Ci	Cil	D

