We will categorise cognition into 7- and 4-level ordinal scales based on DSM-V²² categorisation (Table E).²³ We will calculate scores for cognitive domains using sub-scores of MoCA (or TICS if missing) although we recognise that these global cognitive assessments have some test items that map to a more than one domain, e.g. the

clock drawing test in the MoCA includes aspects of attention, executive function and visual-perceptual function.

- Learning and memory: orientation in place (from MoCA), delayed recall of five word (MoCA), and recall and delayed recall of ten words (TICS)
- Language: using comprehension, semantic and recent memory (from MoCA; similar elements in TICS-M)
- Perceptual-motor function: Cube copy and clock drawing from MoCA
- Executive function: Trail making tests A & B, verbal fluency test (VFT-phonemic)-F (from MoCA); verbal fluency test (VFT-semantic)-animals; clock drawing test (from MoCA); digits forward (from MoCA); digits backward (from MoCA)
- Complex attention: using serial sevens subtraction (MoCA), letter tapping (MoCA)
- Social cognition is not classically assessed in cognitive screening tools and there are no agreed generic short form assessments for social cognition. Aspects of social cognition will be assessed through informant data and NPI-Q although these are not part of the core outcome set.

Table E. Categorisation of cognition based on DSM V with operationalisation (adapted summary from ²³).

	Seven-level categorisation and operationalisation	Four-level categorisation and operationalisation
Normal cognition	No evidence of cognitive impairment (T-MoCA:20-22 AND TICS-m: 25-39)	No evidence of cognitive impairment (T-MoCA:20-22 AND TICS-m: 25-39)
Minor Neurocognitive disorder (mild cognitive impairment)	Single domain Scores are reduced by > 1 point in only one cognitive domain of T-MoCA	Evidence of cognitive impairment (T-MoCA: 15-19 OR TICS-m: 17-24) AND
	Multi-domain Scores are reduced by > 1 point in more than one cognitive domain of T-MoCA	No evidence of functional impairment (mRS <2 OR no change in mRS if pre-stroke mRS >1)
Major neurocognitive disorder	Mild cognitive impairments (T-MoCA 15-19 OR TICS-m 17-23) AND Mild dysfunction (mRS <3)	Persisting cognitive impairment (T-MoCA score <19 OR TICS-m<24 on more than one follow-up) AND Functional impairment (mRS ≥2 or IQCODE >3.6 at final follow-up)

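### SAP 27c–d lets a test on the outcome data replace ordinal regression with an unnamed method, and does not say whether the ordinal result is still reported

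*SAP*

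**What the plan says.** Both documents plan ordinal logistic regression (OLR) for ordinal outcomes. Protocol 9.2 states: "Ordinal logistic regression will be used for ordinal categorical outcomes (e.g. mRS) to increase power". SAP Table D lists the same method, and Table 3 assigns it to mRS and the 7-level cognition scale. SAP section 29 adds: "We will categorise cognition into 7- and 4-level ordinal scales based on DSM-V". Table 9 assigns OLR to several MRI outcomes, including microhaemorrhage counts, SVD score, Fazekas scores, regional WMH change and lacune counts.

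Section 27c says: "The assumption of proportionality will be tested using the likelihood test". Section 27d says that on failure "we will use alternative methods such as multiple logistic regression".

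The SAP separately fixes some binary outcomes. The row "Dependency, mRS>2" is analysed by binary logistic regression (BLR) in Table 3 and also appears in Table 2. Cognitive impairment and a clinical diagnosis of dementia are BLR rows in Table 3. Section 27d refers to none of these.

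**The concern.** The rule makes the reported method depend on a test of the data to be analysed, and leaves the replacement open. Four things are unstated: which proportionality assumption is tested, the test level, the model that takes over, and whether the ordinal result still appears after a failure. If the replacement is a binary logistic model, a 7-level scale offers six cuts and the analyst must pick one after the data are in.

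The nominal 5% level may then not hold for the ordinal outcomes, each of which is compared for ISMN, cilostazol and the combination. Section 17 makes no multiplicity adjustment. SAP section 7 gives avoiding data-driven analyses as a reason for issuing the plan before database lock, and this rule works against that aim.

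**Working it through.** The documents give no error rate for this rule, so there is no figure to reproduce. The check has three parts.

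**1. Which outcomes are caught.** Table 3 says: "Mean (SD) and MLR will be used instead of median [IQR] and OLR for ordinal scales with more than 7 levels". mRS runs from 0 to 6, which is 7 levels, so it stays with OLR. So do the 7- and 4-level cognition scales. MoCA and TICS-m go to linear regression and are unaffected.

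**2. What is fixed and what is open.**

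| Item | Fixed elsewhere? | Linked to 27d? |
|---|---|---|
| mRS cut | Yes, >2 by BLR (Table 3) | No |
| Cut on 7- or 4-level cognition | No; cognitive impairment and clinical dementia are BLR rows, but the former is not tied to one Table E boundary | No |
| Level of the proportionality test | No | – |
| Replacement model | No | – |
| OLR still reported after failure | Not stated | – |

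**3. Size, on the reading that the fallback is a binary cut.** I simulated trials with no treatment effect: 1:1 allocation, a 7-level outcome, no covariates, 6,000 trials per scenario. Each trial had:
- an OLR likelihood-ratio test of treatment;
- a likelihood-ratio test of proportional odds at an assumed 5%;
- a z-test at each of the six cuts.

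If proportional odds passed, the OLR p-value was used. If it failed, either the third cut (for mRS, >2) or the smallest of the six p-values was used. N was 363 (the number recruited, SAP Table 2), 400 (the target), or 182 (about half of 363, for both drugs versus neither).

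Assumed percentages, best to worst level:
- mRS A 20/35/28/9/4/2/2 and mRS B 35/30/18/8/5/2/2. Levels 3–5 total 9+4+2 = 15 and 8+5+2 = 15, matching the 15% dependency in SAP Table A.
- Cognition A 68/8/7/8/5/2/2. Impaired and alive is 8+7+8+5+2 = 30, matching the 30% in Table A.
- Cognition B 40/15/15/15/8/5/2, a more impaired population.

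Results at N = 363 (%):

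| | mRS A | mRS B | Cog A | Cog B |
|---|---|---|---|---|
| Proportionality test fails | 6.5 | 6.3 | 6.7 | 6.2 |
| Type I error, OLR always kept | 4.8 | 5.0 | 5.1 | 5.2 |
| Type I error, switch to fixed cut | 5.7 | 5.6 | 5.5 | 5.4 |
| Type I error, switch to free cut | 9.0 | 8.8 | 8.4 | 8.9 |

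Across N = 363 and 400 the ranges are 4.7–5.4% (OLR kept), 5.1–6.2% (fixed cut) and 8.4–9.8% (free cut). At N = 182 the free-cut range is 8.9–9.4%. Simulation error is about 0.3 to 0.4 points.

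The arithmetic for mRS A at 363 shows where the excess arises. Overall error = P(fail) × P(reject given fail) + the OLR rejections among trials that pass.
- OLR rejections among passing trials: 0.048 − 0.065 × 0.049 = 0.045.
- Free cut after failure: 0.065 × 0.704 = 0.046; total 0.091 (simulated 0.090).
- Fixed cut after failure: 0.065 × 0.178 = 0.012; total 0.057 (simulated 0.057).

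A further distribution (18/30/30/12/6/2/2, N = 363, 3,000 trials) gave a switch in 6.6% of trials and errors of 8.7% (free), 5.9% (fixed) and 5.2% (OLR kept).

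**Covariates.** Section 27b adjusts for eight covariates. With one term each plus treatment, a test of the whole 7-level model checks at least 9 × 5 = 45 constraints, of which only 5 concern treatment. With one binary covariate, N = 363, no treatment effect and 1,500 trials per row (error about 1 point):

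| Covariate | Switch | Free cut | OLR kept |
|---|---|---|---|
| No effect | 7% | 7.9% | 5.1% |
| Log odds ratio 0.2 to 1.1 across cuts | 27% | 11.6% | 4.4% |
| Log odds ratio 0 to 1.5 across cuts | 69% | 16.8% | 5.5% |

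**The case against.** The case for leaving the text alone has several parts.

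- *mRS is already covered.* The >2 cut is pre-specified and reported whatever 27c shows, so another cut would be a visible departure. This stands. What remains is that 27d does not name it as the fallback and does not say that the shift analysis survives.
- *Binary cognition outcomes exist.* True, but neither is tied to 27d, and no boundary is fixed for the ordinal scales.
- *Proportionality may mean proportional hazards.* Table 3 lists a Cox model and BLR together for stroke, and protocol 9.2 plans Cox regression for death. On that reading the fallback needs no cut. The ambiguity is real and is itself something to resolve.
- *Multiple logistic regression may mean a multinomial model,* which needs no cut. This is possible, although Table D lists no regression for nominal outcomes. The replacement would still be unnamed.
- *The stakes are modest.* The primary endpoint is recruitment and retention, which is tabulated. This stands.

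Two stronger readings are tempting. First, a reader might infer an error rate near 20%, because the smallest p-value over six cuts is below 0.05 in 18–22% of the simulated null trials. That figure assumes the best cut is taken in every trial. The plan runs the proportionality test first and keeps OLR when it passes. Second, the SAP says "Use of ordinal measures at the time of analysis will increase statistical power", so a reader might infer that 27d discards power exactly when effects differ across levels. In that situation the common odds ratio has no guaranteed power advantage, and a well-placed cut can do better.

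**Conclusion.** The concern holds in a narrow form. Sections 27c–d state a test-then-switch rule whose trigger is ambiguous and whose replacement is open. For mRS the missing piece is the link to the cut already in Table 3. For the cognition scales no fallback cut exists.

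If the fallback is a freely chosen binary cut, the error of the whole procedure is about 8–10% in place of 5%. This rests on an assumed 5% test level, assumed outcome distributions, no covariates and the least favourable choice of cut. A non-proportional covariate could raise it if the whole adjusted model is tested, by an amount the documents cannot settle. The 4-level scale and the MRI outcomes were not simulated. On the hazards or multinomial readings there is no cut-point inflation, and the problem is lack of specification alone.

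The documents do not support saying that the mRS cut is wholly free, that error reaches about 20% under the plan as written without strong covariate departures, or that the feasibility conclusion is at risk.

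**What to change.** Replace 27c–d with text that does four things:

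1. States which assumption is checked for which outcomes, with proportional odds and proportional hazards treated separately, and the level used.
2. Reports the adjusted common odds ratio from OLR as the planned result for every ordinal outcome, whatever the check shows, described as an average shift across levels.
3. Makes the proportionality check descriptive, so that it does not select the method.
4. Names one supporting analysis per ordinal outcome in advance. For mRS, use >2 by BLR as in Table 3. For cognition, use one Table E boundary that agrees with the definition of cognitive impairment in the composite. Section 26a counts mild impairment and dementia, which points to normal versus anything worse, but 27a omits the word mild, so the team should confirm. A partial proportional odds model is an alternative. For MRI, use an existing BLR row in Table 9 where there is one.

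The cost is a few sentences before final lock, with no new data. The downside is that the common odds ratio is only an average when effects differ across levels, which the supporting analysis would help to show.
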